M
2-20-2015

**Department of Dermatology
University of Minnesota**

Title of Study

Safety and Efficacy of Combined Restylane[®] and Triamcinolone Acetonide 10 mg/cc Intralesional Injections for the Treatment of Alopecia Areata

Purpose

The purpose of this pilot research study is to determine the safety and efficacy of combined hyaluronic acid, Restylane[®], and intralesional Triamcinolone acetonide 10 mg/cc in the management of alopecia areata. Dermal injections of Restylane[®] and triamcinolone acetonide 10 mg/cc will be performed at areas of hair loss on study participants.

Background

AA is an autoimmune organ specific T-cell mediated disease which targets hair follicles and causes non-scarring hair loss⁵. Hairs that are shed are either in telogen or dystrophic anagen⁶. AA can present as patches of alopecia on the scalp, complete loss of hair on the scalp (AA totalis) or loss of hair from the entire body (AA universalis)¹.

This fairly common disorder can affect patients of all ages⁸. Lifetime risk has been estimated to be 1.7%. A significant number of these cases, approximately 7%, may eventually evolve into chronic and severe hair loss⁸. Because the pathogenesis of the disease and the factors contributing to development are not fully understood, predicting the course of the disease is extremely difficult¹. The psychological affects on patients with AA can be devastating. Increased risk of psychiatric disorders such as anxiety disorders (39%) and major depression (39%) have been found in patients affected by the disease³.

With regards to the management of AA, use of IL corticosteroids has become a first line therapy. Synthetic corticosteroids are utilized in

both an anti-inflammatory and immunosuppressive manner, likely controlling the infiltration of T-cells in the perifollicular area by induction of lipocortins¹⁴. Lipocortins antagonize phospholipase A₂ (PLA₂), the enzyme that leads to lysosomal breakdown and release of arachidonic acid in the inflammatory pathway toward the production of inflammatory substances such as prostaglandins, kinins, histamine, liposomal enzymes and complement¹⁵. As a result of this decrease in the amount of inflammatory mediators, inhibition of chemotaxis by vasoconstriction and decreased vascular endothelial permeability results¹⁴. Additionally, these compounds inhibit macrophage and major histocompatibility complexes human leukocyte antigens (MHC HLA) antigen presenting cells¹⁵.

Administration of IL injections of corticosteroids employs injection of triamcinolone acetonide, 3 mg/ml-10 mg/ml typically, administered every 4 to 6 weeks^{12,13}. This method typically involves injection with a 0.5-inch-long 30-gauge needle into the skin at approximately the level of the hair bulb^{12,13}. Regrowth is seen in 4 to 8 weeks and IL corticosteroid injections are then repeated every 4 to 6 weeks. Draw backs and limiting factors of this treatment modality includes atrophy at sites of injections, discomfort and the need for recurrent treatments every 4-6 weeks in patients who cannot sustain hair growth without ongoing therapy. Atrophy of the scalp may also lead to transient cosmetic defects.

Interest in the administration of IL triamcinolone acetonide with hyaluronic acid has developed because of the ability of hyaluronic acid to act as a dermal filler and its reparative properties. Restylane[®], hyaluronic acid, is a high-molecular weight polysaccharide glycosaminoglycan that enhances fibroblast movement and metabolism during wound healing, increasing collagen fibers forming granulation tissue². Hyaluronic acid is known to be important in repair processes such as providing a hydrated, unresisting matrix in which cells are able to migrate⁹.

We hypothesize that Restylane[®] could serve as a repair matrix which also maintains IL triamcinolone acetonide concentrations at higher levels for a longer period of time in the skin, giving a more sustained local anti-inflammatory effect and thus, arresting the AA process and promoting hair regrowth. Furthermore, the combination of Restylane[®]

with IL triamcinolone acetonide injections may prevent a common side, namely, atrophy. With the prevention of scalp atrophy and the preservation of higher concentrations of triamcinolone acetonide for longer periods of time, patient quality of life will be improved, and the expense of medical visits and medications will be reduced as fewer IL corticosteroid injections would be needed each year.

Recent studies investigating the role of peripheral nerves in the pathogenesis of AA have indicated that peripheral nervous system dysfunction exists in the scalp of patients with alopecia areata when compared to normal controls¹⁸. Another mechanism that may account for hair regrowth in AA patients receiving IL hyaluronic acid is that it may provide a regenerative environment for the peripheral nerves of the scalp. Previous studies with hyaluronic acid have demonstrated its ability to facilitate cellular and axonal growth during peripheral nerve regeneration¹¹.

Preclinical Data

The rodent model for the study of AA has not yet been standardized for use in clinical research. Per the President and CEO of the National Alopecia Areata Foundation (NAAF), [name], the work is still in progress to validate the model for clinical testing. Intradermal injections performed in mice often results in subcutaneous injections. Although unpublished, it has been reported to NAAF that several of the rodent models died from unknown reasons during clinical studies.

Preclinical testing in the Dundee experimental bald rat (DEBR) of AA with intralesional injections has proven to be difficult to conduct due to their extremely thin skin.

Clinical Data to Date

Resylane[®] is FDA approved as a medical device in United States for mid to deep dermal implantation for the correction of moderate to severe facial wrinkles and folds such as nasolabial folds. There is no available clinical research data to date investigating the treatment of AA with IL Resylane[®] or its use in the scalp.

In a recent study, eleven healthy human volunteers with photodamaged forearm skin were injected with a hyaluronic acid filler and isotonic

sodium chloride (a vehicle) and skin biopsy specimens were obtained at 4 and 13 weeks¹⁵. It was found that injection of cross-linked hyaluronic acid partially restores dermal matrix components via stimulation of collagen production that had been lost in photodamaged skin. This finding implies that hyaluronic acid has the potential to benefit atrophic skin conditions¹⁵. Thus, AA patients may benefit from both stimulation of therapeutic collagen production in the dermis and collagen production induced by Restylane[®] to prevent scalp atrophy due to AA corticosteroid injections of the scalp¹⁵.

In an ongoing clinical study at the University of Minnesota titled, "Adrenal Function and Use of Intralesional Triamcinolone Acetonide 10mg/ml in Patients with Alopecia Areata," the efficacy of intralesional corticosteroids on hair regrowth in moderate to severe alopecia areata is being evaluated. Subjects undergo intralesional triamcinolone acetonide (10mg/cc) injections every 6 weeks for a period of 6 months, followed by a 6 week, injection-free, safety follow-up visit. Up to 40 mg of triamcinolone acetonide are injected intralesionally at each visit.

Preliminary results from 12 alopecia areata subjects, age ranges 20 to 68, are available. The effects of IL triamcinolone acetonide 10 mg/cc on the hypothalamic-pituitary-adrenal axis in AA patients were recorded. No statistically significant difference in cortisol levels were found from time 0 to 30 minutes following stimulation with triamcinolone acetonide between weeks 0 and 24 (mean difference=0.13). A linear mixed model was also fitted to repeatedly measured cortisol levels (at week 0, 6, 12, 18, and 24) to examine the trend over time. The type III test of coefficient of time variable demonstrated a p-value of 0.99, indicating that cortisol levels from time 0 to 30 minutes following stimulation did not change over time. This data suggests that IL triamcinolone acetonide 10 mg/cc of the scalp does not effect or pose risk to the hypothalamic-pituitary-adrenal axis in AA patients.

In a secondary analysis the alopecia areata severity score (SALT score) was compared between week 0 and week 24 to evaluate hair regrowth using a paired t-test. The mean difference between week 0 and week 24 is 20.4 with standard deviation of 26.5 and is statistically different from zero (p value is 0.03). This indicates that the SALT

score was significantly different between week 0 and week 24, proving that statistically significant hair re-growth was observed as result of treatment with intralesional triamcinolone acetonide 10mg/ml in AA patients.

Methods

Ten subjects (sex ratio not predetermined) ages 18 and older who have extensive alopecia areata of less than 2 years duration will be recruited to participate in this study. Consenting and qualified (meeting the inclusion and exclusion criteria) subjects will participate in this study. This will be a cohort study. The subjects will have three scheduled visits. The total duration of the study for each volunteer is expected to be approximately 12 weeks.

Visti 1.

At the first visit, patients will receive dermal injections of Restylane[®] followed by IL of triamcinolone acetonide, 10 mg/cc, to approximately 20 sites on one half of the scalp. To assess baseline hair growth, photographs and a modified version of the SALT score will be obtained for each side of the scalp. Degree of scalp atrophy, if any, will be recorded. The scalp will also be examined for erythema, scale, folliculitis. Pull tests will be done.

Restylane[®] 0.02-0.04 mL will be injected to the mid dermis, at the level of the hair bulb, in diseased areas on one half of the scalp. Injections will be placed approximately 1 cm apart and will be repeated for up to 3mL of Restylane[®]. When injections have been completed, the injected areas will be massaged.

Using a fine 1 cc syringe and 30 gauge needle, triamincinolone acetonide 10mg/cc will be administered intralesionally to the entire scalp. Injections will be placed approximately 1 cm apart, injecting 0.1 mL Kenalog-10 into the skin at approximately the level of the hair bulb. Injections will be repeated as needed for up to 4 mL Kenalog-10.

Subjects will remain in clinic 20 minutes following the procedure for recording of adverse reactions.

Visit 2.

Subjects will be asked to return for a second visit 5-6 weeks after injections and the visit 1 procedures will be repeated. The SALT score, alopecia areata half head severity score (AAHHSS score), photography and extent of scalp atrophy will be obtained.

Visit 3.

At the third visit, no injections will be given. The SALT score, AAHHSS score, photography, and extent of scalp atrophy will again be obtained.

Adverse experiences will be recorded at each visit.

Schedule of Study Procedures	Visit 1 (Baseline)	Visit 2 (Weeks 5-6)	Visit 3 (Weeks 11-12)
Signed Informed Consent / Assent and HIPAA Authorization (as required)	X		
Demographic Information	X		
Medical History/Review Medications	X	X	X
Assess Inc/Exc Criteria/Consent	X		
Scalp Physical Examination	X	X	X
Record Concomitant Meds	X	X	X
SALT score	X	X	X
AAHHSS	X	X	X
Photography	X	X	X
Assessment of scalp atrophy	X	X	X
Administer Restylane [®] and triamcinolone acetonide 10 mg/cc	X	X	
Record Adverse Experiences	X	X	X

Inclusion criteria

1. Men and women ages 18 and greater.
2. Alopecia areata diagnosis in the last two years with extensive scalp involvement – between 74% and 99%. . Alopecia areata must involve the left and right hemispheres of the scalp.
3. Willing to abstain from use of over the counter products and prescription products other than triamcinolone acetonide 10mg/cc which may promote hair growth.
4. Willing to abstain from the use of non-steroidal anti-inflammatory medications, aspirin, St. Johns Wart, and high doses of Vitamin E supplementation.
5. Subjects must be capable of giving informed consent.
6. Willing to adhere to protocol, including scalp examinations and photography.

The gender of the subjects will not determine enrollment. There is no requirement of male to female ratio for this study. The age range of the subjects will be 18 and greater. No specific racial or ethnic restrictions will be present for this study.

Exclusion criteria

1. Allergy or intolerance to Restylane[®] or hyaluronate preparations
2. Allergy or intolerance to triamcinolone acetonide, 10 mg/cc.
3. Underlying disease that might be adversely affected by Restylane[®] or triamcinolone (ex. patients with bleeding disorders).
4. Immunosuppressed patients (history of transplantation, cancer, chemotherapy, splenectomy, HIV).
5. Pregnant or lactating female.
6. Application of topical immunomodulatory or immunosuppressive agent in the preceding 6 weeks.
7. Systemic administration of corticosteroid or other systemic treatment (i.e. prednisone) that has immunomodulatory or other immunosuppressive mechanism of action, in the preceding 8 weeks.
8. Clinical evidence of secondary skin infection (i.e., folliculitis).

9. Other inflammatory or infectious skin disease that might interfere with evaluations during the study.
10. Investigational medications within the past 30 days.
11. Investigational medications within the past 30 days.
12. Patients with susceptibility to keloid formation.
13. Severe allergies manifested by a history of anaphylaxis, or history or presence of multiple severe allergies
14. Patients with allergies to gram positive bacterial proteins
15. Unable to give consent.

During the study period, subjects will be allowed to apply non-medicated shampoos to the scalp.

Statistical Plan

Sample size:

We plan to study 10 subjects. This is a pilot study. The reasoning for sample size selection is to proceed with preliminary studies in a small group. All subjects will be selected based on inclusion and exclusion criteria.

Data Collection:

Data for this study will be entered into a REDCap database, which uses a MySQL database via a secure web interface with data checks used during data entry to ensure data quality. REDCap includes a complete suite of features to support HIPAA compliance, including a full audit trail, user-based privileges, and integration with the institutional LDAP server. The MySQL database and the web server will both be housed on secure servers operated by the University of Minnesota Academic Health Center's Information Systems group (AHC-IS). The servers are in a physically secure location on campus and are backed up nightly, with the backups stored in accordance with the AHC-IS retention schedule of daily, weekly, and monthly tapes retained for 1 month, 3 months, and 6 months, respectively. Weekly backup tapes are stored offsite. The AHC-IS servers provide a stable, secure, well-maintained, and high-capacity data storage environment, and both REDCap and MySQL are widely-used, powerful, reliable, well-supported systems. Access to the study's data

in REDCap will be restricted to the members of the study team by username and password.

Statistical Analysis:

Data will be analyzed for safety and efficacy of administration of IL triamcinolone acetonide 10 mg/cc and Restylane® in the management of (alopecia areata) AA.

The primary endpoint of evaluating the efficacy of administration of IL triamcinolone acetonide 10 mg/cc and Restylane® in the management of AA is the alopecia areata half head severity score (AAHHSS) comparing week 12 with baseline hair loss. The primary analysis will be a comparison of means of AAHHSS between two treatments on the two sides of AA patients scalp using paired t-tests.

The secondary analysis will examine the mean trend over time for the AAHHSS and SALT score at weeks 0, 6, and 12 using linear mixed models (specifically, using the MIXED procedure of the SAS system, version 9.2) with time after baseline as the fixed effect and using the repeated-measures option of the MIXED procedure.

Safety will be analyzed through determination of the frequency of side effects and/or adverse events recorded during the study.

Supportive analyses will examine the demographic and baseline characteristics of the study sample. Descriptive statistics including either numerically or graphical representations will be used to summarize the data.

Primary Study Endpoints

To assess the efficacy of IL Restylane® and triamcinolone acetonide 10 mg/cc in the management of AA, baseline hair growth will be recorded via photographs of the scalp and the SALT score and AAHHSS score. Subjects will be asked to return for a second visit at 5-6 weeks for injections. Markers of hair regrowth include the SALT score, the AAHHSS score and photography.

The Severity of Alopecia Tool (SALT) score measures the percentage hair loss at each visit¹⁹. The SALT score is determined through a visual examination of 4 views of the scalp; the percent of terminal hair loss visible in each area is recorded and then aggregated, with a maximum SALT score of 100 corresponding to 100% scalp hair loss¹⁹. In this study, the AAHHSS score will be used to determine hair loss on each half of the scalp when the scalp is divided in the sagittal plane. Each half of the scalp may have a maximum score of 50.

The primary efficacy endpoints are as follows, ranked in order of importance:

1. The AAHHSS will be used to compare hair regrowth on each side of the scalp at 0, 6 and 12 weeks.
2. The SALT score will be used to assess hair regrowth throughout the entire scalp at weeks 0, 6, and 12.

Secondary Study Endpoints

To assess the safety of intralesional Restylane[®] and triamcinolone acetonide 10 mg/cc in the management of alopecia areata scalp examinations will be performed before treatment, immediately after treatment and at 5-6 weeks follow up. Medication side effects and adverse experiences will be recorded. Additionally, subjects will be given a telephone contact number to report side effects anytime after visit 1.

Degree of scalp atrophy will be assessed by the principal investigator and be recorded for comparison across visits.

Medication, Dosing and Dose Rationale

At visit 1, Restylane[®] will be delivered by IL injection into the dermis of the diseased scalp. The minimum and maximum dose of Restylane[®] will be 1mL and 3mL, respectively. The dose of Restylane[®] does not exceed the recommended maximum dose per treatment. Based on clinical U.S. studies on the use of Restylane[®] as a dermal filler for correction of moderate to severe facial wrinkles, the

recommended maximum dose is 6mL. Restylane® will be injected throughout the diseased area by serial puncture. IL injections will be spaced approximately 1cm apart, administering approximately 0.02-0.04mL at each site.

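### The protocol does not say how the Restylane half of the scalp is chosen; randomising left or right per patient would protect the only controlled comparison at almost no cost

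*Combined protocol and SAP*

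**What the plan says.** Under Methods, Visit 1, Restylane is given "in diseased areas on one half of the scalp" and triamcinolone is given across the whole scalp. Visit 2 repeats the Visit 1 procedures without saying that the same half is treated. The Methods section describes the design in one sentence: "This will be a cohort study". No readable text mentions randomisation, alternation, a fixed side, or a rule based on the worse or better half. One figure and the consent pages are not available, but nothing readable points to an allocation rule there.

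Inclusion criterion 2 requires 74% to 99% scalp involvement and adds: "Alopecia areata must involve the left and right hemispheres of the scalp". It does not require the halves to be equally affected. At Visit 1 "photographs and a modified version of the SALT score will be obtained for each side of the scalp". The same visit covers other features: "Degree of scalp atrophy, if any, will be recorded", and "Pull tests will be done".

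Under Statistical Analysis, the primary endpoint is the half-head score (AAHHSS) "comparing week 12 with baseline hair loss". The primary analysis is a "comparison of means of AAHHSS between two treatments on the two sides of AA patients scalp using paired t-tests". No baseline adjustment is stated for it.

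**The concern.** The half-against-half contrast is the only efficacy comparison with a concurrent control. SALT is followed over time for the whole scalp, and atrophy is compared across visits. Pairing removes differences between patients, but not the effect of how the treated half was chosen within a patient.

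The half scores, atrophy and pull test are all obtained at the injection visit, so whoever picks the half may know them. If the worse half tends to be treated, two things follow:

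- **Change from baseline** (the more natural reading of the endpoint sentence) favours Restylane. A higher starting score has more room to fall, and part of a high observed score is rating error that does not recur.
- **Week-12 scores** count against Restylane, because the treated half started worse.

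Treating the better half reverses both. A reader could not tell which way a reported difference leans.

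The choice could also follow features that AAHHSS does not measure. Preventing atrophy is part of the Restylane hypothesis in the Background, so atrophy is one plausible candidate. In a 10-patient pilot, what is at stake is mainly an unbiased estimate for planning the next study; type I error is a secondary yardstick.

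**Working it through.** The plan gives no power or sample-size calculation, so there is no design figure to reproduce.

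**1. Room for imbalance.** If the two half scores (maximum 50 each, Primary Study Endpoints) add to the whole-scalp score, the largest eligible gap is 50 − (T − 50) = 100 − T for total loss T. At T = 74 this is 26 points (50 against 24); at T = 99 it is 1 point. The 26-point gap is the extreme case.

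**2. Simulation inputs.**
- From the documents: n = 10, T between 74 and 99, maximum 50 per half.
- Borrowed: the University of Minnesota study under Clinical Data to Date reports a mean SALT change of 20.4 (SD 26.5) at week 24, with no baseline. Dividing by an assumed baseline of 86.5, the midpoint of 74 and 99, gives regrowth of 20.4/86.5 = 23.6%, SD 26.5/86.5 = 30.6%.
- Assumed: T uniform; SD of the observed half-to-half difference 4.4, 6.5 or 9.1 points; rating-error SD 2; between-half regrowth SD 10%.
- No true Restylane effect; two-sided 5% paired t-test; 20,000 trials per case. The worse half is the one with the higher observed baseline score.

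**3. Results.** Ranges run over the three half-difference SDs. Positive bias favours Restylane.

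| Worse half treated in | Bias, change (points) | Type I error, change | Bias, week 12 (points) | Type I error, week 12 |
|---|---|---|---|---|
| Random half | about 0 | about 5% | about 0 | about 5% |
| 60% | +0.4 to +0.6 | about 5% | −0.3 to −0.8 | about 5% |
| 70% | +0.8 to +1.2 | 6–8% | −0.6 to −1.6 | 6–9% |
| 80% | not tabulated | 9–11% | not tabulated | 7–13% |
| 90% | not tabulated | 12–16% | not tabulated | 7–21% |
| 100% | +2.1 to +2.9 | 16–22% | −1.4 to −4.1 | 9–32% |

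For scale, an assumed extra 10 percentage points of regrowth is 0.10 × 86.5/2 = 4.3 points per half. The standard error of the 10-patient mean difference is about 2.1 to 2.7 points.

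**4. Sensitivity.** Varying the borrowed baseline from 50 to 99 gives, for change and week-12 scores respectively, 5–9% and 4–9% at 60–70% preference, and 14–39% and 7–34% if the worse half is always treated. A random half stays at about 5%. A second model used different assumptions: true half-difference SD 2, 5 or 10; rating-error SD 1, 2 or 4; SD of the half-to-half difference in change 4. Always choosing by severity then gave 5.2–33% on change and 5.7–88% on week-12 scores, against about 5% for a random half.

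**5. Would baseline adjustment be enough?** Regressing the week-12 half difference on the baseline half difference and testing the intercept held type I error at 4.3–5.3% in all the severity-driven cases of step 3. Power at an assumed 20 percentage points of extra regrowth was 82–85% with a random half, 78–80% at 70% preference and 46–51% if the worse half is always treated. Adjustment does not remove choice on a feature outside AAHHSS. With an assumed correlation of 0.3–0.5 between that feature and the half's regrowth, adjusted type I error was 5–6% at 70% preference (bias 0.5–0.8 points) and 8–15% if the feature is always followed (bias 1.2–2.1 points).

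**The case against.** What is established is an unstated rule, not a biased choice. The text also fits a coin toss, alternation, or one fixed side for everyone. A fixed side would not select on severity, though it would tie treatment to left or right. This stands, and it limits the claim to possible bias.

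At 60–70% preference the bias of 0.3 to 1.6 points is smaller than the pilot's standard error of 2.1 to 2.7 points, and the larger error rates need the worse half treated in nearly every patient. This also stands. It is why the case does not rest on the worst-case figures.

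The concern about features outside AAHHSS is partly speculative. The protocol does not say that atrophy or pull tests are recorded per side or guide the choice, and the correlations are assumed.

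Randomisation leaves chance imbalance. With independent allocation, the worse half would be treated in at least 7 or at most 3 of 10 patients with probability 2 × (120 + 45 + 10 + 1)/1024 = 34%. That is chance error, which the test allows for, rather than systematic bias. Baseline adjustment remains useful alongside randomisation.

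The point scale is itself uncertain. The worksheet weights for one side (0.36 + 0.40 + 0.24) sum to 1.00, which suggests a maximum of 100 per half rather than 50. That would change the point figures above, but not the gap in the design or its remedy.

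**Conclusion.** The concern holds as a matter of design. The only controlled efficacy contrast depends on a choice of half that the readable protocol leaves open, made at the visit where both halves are scored, and the planned test does not adjust for it. Confidence is high that the rule is missing. Whether bias would arise, and how large it would be, is unknown. Under the stated assumptions the effect runs from negligible at 60% preference to type I error of 16–22% (change) or 9–32% (week-12 scores) if the worse half is always treated. These figures are illustrations that depend on borrowed and assumed inputs and on the 50-point reading of AAHHSS. The point should be fixed before enrolment, because analysis can only partly repair a selected side afterwards.

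**What to change.** In Methods, Visit 1, state that the Restylane half (left or right) is randomised for each patient, for example five left and five right. Use a concealed list, held in REDCap or sealed envelopes, and open each assignment only after eligibility, baseline AAHHSS and photographs are recorded. State that the allocated half stays the same at Visit 2. Describe the design as a randomised within-patient (split-scalp) study instead of a cohort study.

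Adjustment for per-side baseline AAHHSS is a reasonable addition, and the fallback if randomisation is not adopted. Randomisation does not address rater bias, since no blinded scoring of the halves is described.

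The cost is a few sentences and a 10-line list, plus someone to generate and hold it. REDCap is already planned for data entry, though the protocol does not mention using it for allocation. Sample size, visits, injections and the paired test are unchanged. The one thing given up is the freedom to choose the half.

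### The primary paired test estimates what Restylane adds to triamcinolone, while the aim is worded as efficacy of the combination; the time-only model and whole-scalp SALT mix the two treatments

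*Combined protocol and SAP*

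**What the plan says.** **Allocation.** Methods, Visit 1 places Restylane in one half of the scalp and triamcinolone over the whole scalp. Medication, Dosing and Dose Rationale confirms that triamcinolone is bilateral, up to 2 mL per side and 4 cc in total, scaled to lesion size. The halves are therefore Restylane plus triamcinolone, and triamcinolone alone. The opening Visit 1 sentence, and the dosing text on where Restylane is injected, are worded more loosely, but the detailed procedure settles it.

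**Aim.** The Purpose is to "determine the safety and efficacy of combined hyaluronic acid" and triamcinolone. Statistical Analysis speaks of "The primary endpoint of evaluating the efficacy of administration of IL triamcinolone acetonide 10 mg/cc and Restylane® in the management of AA", and Primary Study Endpoints opens with "To assess the efficacy of IL Restylane® and triamcinolone acetonide 10 mg/cc in the management of AA".

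**Analyses.** The primary endpoint is AAHHSS, "comparing week 12 with baseline hair loss". The primary test is "The primary analysis will be a comparison of means of AAHHSS between two treatments on the two sides of AA patients scalp", by paired t-tests. The secondary mixed models for AAHHSS and SALT are specified "with time after baseline as the fixed effect". No other fixed effect is named.

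**Ranked primary efficacy endpoints.** First: "The AAHHSS will be used to compare hair regrowth on each side of the scalp at 0, 6 and 12 weeks". Second: "The SALT score will be used to assess hair regrowth throughout the entire scalp at weeks 0, 6, and 12".

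**The concern.** Three sections ask whether the combination works, but the primary test asks whether Restylane improves on triamcinolone alone. These questions can have different answers, because triamcinolone is expected to produce regrowth by itself.

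The practical risk lies mainly in the supporting results. Whole-scalp SALT is ranked second among the primary efficacy endpoints, under an objective worded as efficacy of the combination. A fall in SALT, or a time trend in AAHHSS with no side term, could be credited to the combination although part of it comes from a half that had no Restylane. The Clinical Data to Date section already treats an uncontrolled before-after SALT change as proof of a treatment effect, so this reading is not far-fetched. In a pilot of 10 subjects, the main product is what it tells the next study, and there the increment and the total change need to be kept apart.

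**Working it through.** The plan gives no effect size, SD, alpha or power for this contrast, so there is no design figure to reproduce. The check is algebra on the allocation, with an illustration.

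**Definitions.** Let T be the AAHHSS improvement from baseline to week 12 on the triamcinolone-alone half, and R the extra improvement on the Restylane half. R includes any steroid-prolonging effect. This assumes comparable halves and similar steroid dose per side.

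- Combination half's own change: T + R.
- Paired difference in change: (T + R) − T = R. T cancels.
- Time-only model fitted to both halves' AAHHSS: (T + (T + R))/2 = T + R/2.
- Whole-scalp SALT, if two halves with a maximum of 50 each sum to 100: T + (T + R) = 2T + R.
- Model with side and side-by-time: the week-12 change is T on the triamcinolone-alone half, and the interaction is R, so both are reported separately.

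**Illustrative inputs.** Clinical Data to Date reports a mean SALT improvement of 20.4 (SD 26.5, 12 subjects) from week 0 to week 24 on triamcinolone 10 mg/mL alone. Split evenly, that is 20.4/2 = 10.2 per half. The share reached by week 12 is not given. I take 10.2 × 12/24 = 5.1 (linear in time) up to 10.2 (all by week 12). R is not given either; 0 and 5 are assumptions.

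| Quantity | R = 0 | R = 5 (assumed) |
|---|---|---|
| Combination half, T + R | 5.1 to 10.2 | 10.1 to 15.2 |
| Paired difference, R | 0 | 5 |
| Time-only model, T + R/2 | 5.1 to 10.2 | 7.6 to 12.7 |
| Whole-scalp SALT, 2T + R | 10.2 to 20.4 | 15.2 to 25.4 |

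At R = 0, SALT improves by 10.2 to 20.4 points with no contribution from Restylane. At R = 5, none of the last three rows equals the combination half's own change.

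**Scale caveat.** Primary Study Endpoints gives each half a maximum of 50. The worksheet weights sum to 0.36 + 0.40 + 0.24 = 1.00 per side, which suggests 0 to 100 per half. On that scale T would double to 10.2 to 20.4, and SALT would be the average of the halves. The cancellation of T, and the mixing in SALT and the time-only model, do not depend on the scale.

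**Which variable is paired.** The endpoint is defined against baseline, but the primary analysis sentence compares mean AAHHSS without saying whether this is the week-12 score or the change. If the halves differ at baseline, the week-12 difference carries that imbalance; the difference in change removes it.

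**The case against.** The strongest reply is that the test is the right one. Intralesional steroid is described as first-line, the Background hypothesis is that Restylane prolongs its effect and prevents atrophy, and judging a combination against its standard component is a normal meaning of efficacy. This stands. A reader might infer that the primary test is invalid or should be replaced; the documents do not support that.

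A reader might also infer that a null paired test would hide regrowth on both halves. It would not: at R = 0 the planned SALT and time trends would show the regrowth beside it.

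A third inference is that the combination half's result is unavailable under the plan. That too goes beyond the text. AAHHSS exists only by half, the endpoint is set against baseline, the t-tests are plural, and descriptive statistics are planned. Fitting both halves in one time-only model is one reading; no sentence orders pooling. On the 0 to 50 scale the figure can even be recovered from planned results, if the paired test uses change: (SALT change + paired difference)/2 = (2T + R + R)/2 = T + R, for example (15.2 + 5)/2 = 10.1. What remains is that no by-half analysis is specified and the named model cannot address the treatment contrast.

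Two further points stand. The numbers are illustrations only. And the added effect is not that of the gel alone: the Restylane half also has extra punctures, and massage is described only for it, so the contrast is for the whole procedure.

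**Conclusion.** The primary paired test is a sound add-on contrast. It does not estimate efficacy of the combination, which is how the Purpose, Statistical Analysis and Primary Study Endpoints sections word the question. Regrowth in whole-scalp SALT, or in an AAHHSS trend with time as the only fixed effect, mixes the two treatments and cannot be credited to the combination. A by-half analysis is open to the investigators but not written down.

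This is a cheap improvement to the plan, not a fault that invalidates it. The structural conclusion rests on the allocation alone. Reading R as the procedure's effect also needs comparable halves and similar steroid dose; dosing follows lesion size, so similarity is not guaranteed. The point values depend further on the assumed R, the week-12 timing and the 0 to 50 half scale. Even the combination half's own change would be uncontrolled, so it describes regrowth and cannot establish efficacy.

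**What to change.** 1. In Statistical Analysis, name the two halves by treatment. State the primary objective and conclusion as the added effect of the Restylane procedure, including its extra punctures and massage, over triamcinolone alone. Test it by a paired t-test on each half's AAHHSS change from baseline to week 12. Align the Purpose and Primary Study Endpoints wording.
2. Add side (Restylane half against the other) and side-by-time as fixed effects in the AAHHSS mixed model, with a covariance structure that accounts for both halves belonging to the same subject. Report each half's change, and label the combination half's change as uncontrolled and descriptive.
3. Treat whole-scalp SALT as descriptive, not as evidence of combination efficacy.

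While editing, bring the opening Visit 1 sentence and the Restylane dosing text into line with the allocation; this is clerical.

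The cost is some wording and two model terms. Data, visits, doses and sample size do not change. The downside is a narrower efficacy claim.
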